4.6 Total number of devices intended for the clinical investigation

72 subjects will be included in the study. Subjects will be supplied with sufficient amount of test products to accommodate their usual catheterisation procedure for each test period. The investigational devices and comparators are packed in retail boxes with 30 products in each.

Example: The test period (home-use) is 2 weeks (14 days) and with an estimated usage of 6 catheters/day it equals 84 catheters, so subject will receive 3 retail boxes for home use (90 catheters) for each test period.

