5.1 General

The investigation is a multi-centre, multi-national, randomised, controlled crossover study including 72 female IC users.

The total study duration for the individual subject will be approximately 4 weeks, consisting of four site visits and two 2-week test periods (T1 and T2) at home (+/- 3 days). Visits 0 and 1 can be performed on the same day. One self-catheterisation will be done at visit 1 with the first randomised product. For visit 2 and 3, two catheterisations (HCP and a self-catheterisation) will be performed in a hospital setting for bladder emptying assessment at each visit. At visit 2 the catheterisations will be done with the first randomised product, and at visit 3 the catheterisations will be done with the second randomised product. Test periods (at home) take place directly following visit 1 and 2. No data will be collected in the test periods at home. Visit 3 will terminate the study.

The study design and procedures are described below in figure 1.

[figure not shown]

Figure 1. Study design

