- Introduction to 1st randomly assigned product, including IFU.
- Self-catheterisation (with 1st randomly assigned product)
- Catheterisation position noted [Sitting/standing]
- Catheter used for catheterisation noted [investigational product/comparator, including product size (CH12/CH14)]
- Catheter handed out for the first test period is noted [investigational product/comparator, including product size (CH12/CH14)]
- Scheduling Visit (V2), 14 days (+/-3 days) days after Baseline Visit (V1)
- Complete eCRF

Test Period 1 (T1):

The two weeks of home-use with the first randomly assigned product according to an individual usage regime. No data will be collected during the home period.

Visit 2 (V2) – Catheterisation, follow-up and introduction to T2

The subject should not have changed their medication the last 24 hours before V2 or show symptoms of UTI (assessed by investigator). If signs of UTI, they must be rescheduled and registration of AE.

- Ask for change in relevant medical history since last visit.
- Review of Adverse events/Serious adverse events/Adverse device events, Device deficiencies and Protocol Deviations
- Review of changes in concomitant medication
- Assessment on user perception for Test Period 1.

HCP-Catheterisation:

- Pre-catheterisation volume [mL] measured in triplicate with a bladder scanner. All three measurements must be above 150 ml to proceed. If not subject is asked to intake fluid and wait until bladder volume is ≥ 150 ml.
- Catheterisation with the 1st randomly assigned product used in T1 will be performed by HCP. NB! HCP should wait for 3 sec. when suspicion of flow-stop before rotating catheter to make it more clear on the profile from the databox.
- Catheter used for catheterisation [investigational product/comparator, including product size (CH12/CH14)], position [Sitting/standing], and time for start of catheterisation is noted.
- Urine volume at 1st flow stop [g] and post catheterisation [g] is noted.
- Number of flow stops is noted.
- All assessments pertaining to performance, including catheterisation profile, will be recorded at the catheterisation.
- Residual volume [mL] will be measured in triplicate with bladder scanner after catheterisation is completed.
- After first catheterisation subjects will be asked to intake fluid and wait in the waiting room to ensure there is urine in the bladder before the second catheterisation.

Self-Catheterisation:

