- Pre-catheterisation volume [mL] measured in triplicate with a bladder scanner. All three measurements must be above 150 ml to proceed. If not subject is asked to intake fluid and wait until bladder volume is ≥ 150 ml.
- Catheterisation with the 1st randomly assigned product used in T1 will be performed by subject. Subject should wait for 3 sec. when suspicion of flow-stop before rotating catheter to make it more clear on the profile from the databox.
- Catheter used for catheterisation [investigational product/comparator, including product size (CH12/CH14)], position [Sitting/standing], and time for start of catheterisation is noted.
- Urine volume at 1st flow stop [g] and post catheterisation [g] is noted.
- Number of flow stops is noted.
- All assessments pertaining to performance, including catheterisation profile, will be recorded at the catheterisation
- Residual volume [mL] will be measured in triplicate with bladder scanner after catheterisation is completed.
- After completed self-catheterisation, subjects are asked to assess any level of discomfort during catheter insertion, during emptying of bladder, at the end of emptying and at withdrawal of catheter (evaluated on the visual analogue scale (VAS) [cm]). VAS scores are asked to be rated immediately after withdrawal of catheter.
- Introduction to 2nd randomly assigned product, including IFU.
- Schedule V3 within 28 days (+/- 3 days) after V1
- Complete eCFR

Test period 2 (T2)

The two weeks of home-use with the second randomly assigned product according to an individual usage regime.

Visit 3 (V3) – Catheterisation, follow-up, and termination

The subject should not have changed their medication the last 24 hours before V2 or show symptoms of UTI (assessed by investigator). If signs of UTI, they must be rescheduled and registration of AE.

- Ask for change in relevant medical history since last visit.
- Review of Adverse events/Serious adverse events/Adverse device events, Device deficiencies and Protocol Deviations
- Review of changes in concomitant medication
- Assessment on user perception for Test Period 2.

HCP-Catheterisation:

- Pre-catheterisation volume [mL] measured in triplicate with a bladder scanner. All three measurements must be above 150 ml to proceed. If not subject is asked to intake fluid and wait until bladder volume is ≥ 150 ml.

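### Both V2 and V3 are timed from V1 with no V2-to-V3 interval, so the second home period can run 8 to 20 days against the 11 to 17 days that section 5.1 states

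*Combined protocol and SAP*

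**What the plan says.** **Length of the home periods.** Section 5.1 describes "two 2-week test periods (T1 and T2) at home (+/- 3 days" and adds: "Test periods (at home) take place directly following visit 1 and 2". T2 therefore starts at V2 and ends at V3. Section 7.2 describes T2 as "The two weeks of home-use with the second randomly assigned product according to an individual usage regime".

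**Visit timing.** Section 7.2 has, at V1, "Scheduling Visit (V2), 14 days (+/-3 days) days after Baseline Visit (V1", and at V2, "Schedule V3 within 28 days (+/- 3 days) after V1". Table 2 (section 7.3) agrees: V1 on day 0, V2 on day 14 ± 3, V3 on day 28 ± 3. Neither place sets an interval from V2 to V3.

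**Rescheduling.** For V2, section 7.2 says: "If signs of UTI, they must be rescheduled and registration of AE". The same rule appears at V3. No limit is put on the delay, and nothing says whether V3 moves when V2 does.

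**Outcomes tied to the home periods.** The number of adverse events is a secondary endpoint (5.3). Perception is a secondary objective (3.1) but an exploratory endpoint (5.4), and the questionnaire asks about the home period just ended. Section 10.1 presents summaries by device. Sections 10.4 to 10.6 plan listings or summaries of these data, with no time at risk as a denominator.

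**Supply.** Section 4.6 works an example for a 14-day period: "estimated usage of 6 catheters/day it equals 84 catheters, so subject will receive 3 retail boxes for home use (90 catheters". It also requires that each subject receive enough product for her usual use.

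**The concern.** In a crossover the two products should be used for about the same time. Section 5.1 sets a limit on each home period, but the instructions that a site follows when booking visits enforce that limit only for the first. Because V2 and V3 each float around a date fixed by V1, T2 takes up the variation of both visits.

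Three things are at stake.

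- **Adverse event counts per device.** A count over 8 days and a count over 17 days are not comparable without days of exposure, and none are planned.
- **Perception.** The answers for the two products may rest on quite different lengths of use.
- **Dependence on an outcome.** If a UTI in the first period delays V2 and V3 does not move, T1 grows and T2 shrinks because of something that happened on the first product. Randomising the order does not remove that kind of imbalance.

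A lesser consequence concerns the per-protocol set. A woman with an 8-day T2 has followed section 7.2 but not section 5.1. Section 13 treats any variance from the protocol as a deviation, and section 10.2 defines the per-protocol set by treatment as planned, so her status depends on which section is read.

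**Working it through.** **Inputs**

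- Stated period length: 14 ± 3 = 11 to 17 days (5.1).
- V2: day 14 ± 3 after V1 = day 11 to 17 (7.2, Table 2).
- V3: day 28 ± 3 after V1 = day 25 to 31 (7.2, Table 2). The wording in 7.2 is loose, but Table 2 supports this reading.
- T2 length = V3 day − V2 day (5.1).

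**1. The plan's own figure.** The supply example reproduces: 14 days × 6 per day = 84; three boxes of 30 = 90.

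**2. Range of T2 with both visits in window**

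- Shortest: 25 − 17 = 8 days (T1 is then 17 days).
- Longest: 31 − 11 = 20 days (T1 is then 11 days).

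| V2 day | T2 allowed by the V3 window (days) | Whole-day values outside 11–17 |
|---|---|---|
| 11 | 14–20 | 3 (long) |
| 12 | 13–19 | 2 (long) |
| 13 | 12–18 | 1 (long) |
| 14 | 11–17 | 0 |
| 15 | 10–16 | 1 (short) |
| 16 | 9–15 | 2 (short) |
| 17 | 8–14 | 3 (short) |

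There are 7 × 7 = 49 combinations; 12 fall outside 11 to 17, six on each side. This counts combinations and is not a probability.

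**3. Can both limits be met together?** Yes, for every in-window V2. With V2 on day 11, V3 on days 25 to 28 satisfies both. With V2 on day 17, V3 on days 28 to 31 does.

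**4. V2 delayed by a UTI, V3 kept in its V1-based window.** With V2 on day 17 + x, T2 runs from 25 − (17 + x) = 8 − x to 31 − (17 + x) = 14 − x days. The upper end falls below 11 when x > 3, that is, when V2 is later than day 20.

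- V2 on day 20: at most 31 − 20 = 11 days, still within 5.1.
- V2 on day 21: 4 to 10 days.
- V2 on day 24: 1 to 7 days.

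The delays to days 21 and 24 are illustrative assumptions.

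**5. How many women might this touch?** Section 2 cites 0.8 to 3.5 catheter-associated UTIs per year. If that range applied here, 72 women over 14 days would have 72 × 14/365 × 0.8 = 2.2 to 72 × 14/365 × 3.5 = 9.7 events in T1. Only those still present at V2, and slow enough to clear to push V2 past day 20, would force a short T2. The number is therefore a handful at most.

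**6. Supply, as a side note.** 90 / 6 = 15 days, whereas 17 days at 6 per day needs 102. At 5 per day, 90 catheters last 18 days; at the eligibility minimum of 3 per day, 30 days.

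**The case against.** The strongest reply is that the two limits do not conflict. A site can read the V3 window as a second condition on top of section 5.1, and step 3 shows that both can then always be met. Of the 49 combinations, 37 already comply, and 8 and 20 days need the visits at opposite ends of their windows. This stands as a limit on the size of the problem. It does not remove it, because the booking instruction and the flow-chart, which sites work from, carry no T2 limit.

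Four stronger readings are tempting, and the documents do not support them.

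- **Each day of delay at V2 is lost from T2.** The V3 window gives slack up to day 20, and the plan never says that V3 stays fixed. It also reschedules V3 itself for signs of UTI, which would lengthen T2.
- **Only the second product's exposure varies.** T1 also ranges over 11 to 17 days and lengthens when V2 slips. The four sequences in section 5.8 have equal shares, so the investigational device comes second in half the subjects and a wider T2 is, on average, balanced between devices. A device bias would need UTI rates that differ by device, which nothing here shows.
- **Subjects will run out of product.** The 90 catheters are a labelled example, and the rule in 4.6 is sufficient supply for the individual.
- **The primary comparison is compromised.** Residual volume at first flow-stop is measured at V2 and V3, and section 5.1 has no data collected at home.

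It is also fair to say that no between-device test is planned on adverse events or perception. The issue is how the descriptive comparisons are read.

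**Conclusion.** The inconsistency is real and modest. As scheduled, T2 can last 8 to 20 days with both visits in window, against 11 to 17 stated. If V2 slips past day 20 and V3 stays tied to V1, T2 cannot reach 11 days. The first statement follows from the text alone. The second rests on an assumption about V3 on which the plan is silent.

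The consequence is confined mainly to the per-device adverse event and perception summaries, which would rest on unequal exposure that in a few women may depend on a UTI during the first product's period. The effect on the primary endpoint is probably small. How far actual T2 lengths would spread cannot be known from the documents, since they give no distribution of visit dates.

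**What to change.** - Reconcile sections 5.1, 7.2 and Table 2 so that the visit schedule itself enforces the stated T2 length. Two ways would do it. Timing V3 at 14 ± 3 days from the actual V2 date gives T2 of 11 to 17 days by construction, with V3 on day 22 (11 + 11) to day 34 (17 + 17) after an in-window V2. Keeping the V1-based window and adding the section 5.1 limit on T2 holds V3 to days 25 to 31, but cannot be met once V2 is later than day 20. The choice is the sponsor's.
- State what happens to V3 when V2 is rescheduled.
- In sections 10.4 and 10.6, report adverse events with days of exposure per device, and tabulate the lengths of T1 and T2 by device.
- Optionally, note in section 4.6 that the worked example covers 15 days at 6 per day and not the 17 days that section 5.1 allows.

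The cost is a few lines of text and one extra summary. Some subjects would finish a few days later.

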7.3 Flow-chart

Table 2. Chart showing the connection between visits and assessments.

Visit(V)	V0	V1	V2	V3 (EoT)
Timing of visit (Days)	0	0	14 (± 3)	28 (± 3)
Activity				
Introduction to investigation and review of Subject Information Form/Informed Consent Form	X			
Signed Informed Consent		X		
Allocation of subject number in eCRF		X		
Check of in- and exclusion criteria		X		
Pregnancy test (urine dipstick) – for subjects of childbearing potential only		X		
Baseline information		X		
Concomitant medication related to urinary function and pain management assessed by PI		X	X	X
Relevant medical history assessed by PI		X	X	X
Randomisation		X		
Training in use of investigational device		X	X	
Hand out investigational devices and supplementary supplies		X	X	
Perform device accountability		X	X	X
Subject to complete perception questionnaire based on home period			X	X
HCP catheterisation			X	X
Bladder scan before and after catheterisation			X	X
Recording of catheterisation profile (data box)			X	X
Position, catheterisation start time and catheter registered			X	X
Urine volume at 1 st flow-stop (scale)			X	X
Urine volume measured post catheterisation (Scale)			X	X
Number of flow-stop episodes counted by HCP			X	X
Self-Catheterisation	X	X	X	
Bladder scan before and after catheterisation			X	X
Recording of catheterisation profile (data box)			X	X
Position, catheterisation start time and catheter registered			X	X
Position and catheter registered	X			
Urine volume at 1 st flow-stop (scale)			X	X
Urine volume measured post catheterisation (Scale)			X	X
Number of flow-stop episodes counted by HCP			X	X
Subject to complete discomfort on VAS (only self-catheterisation)			X	X
Subject to complete perception questionnaire based on home period			X	X
AEs/ADEs/SAEs/SADES		X	X	X
Device deficiencies		X	X	X
Protocol deviations		X	X	X
Complaint handling (Vigilance form)		X	X	X
Complete eCRF		X	X	X
Termination form				X

7.4 Case Report Forms

All assessments and observations throughout the investigation for each subject must be carefully recorded in an electronic CRF (eCRF).

CRFs will be filled in by the principal investigator and/or delegated site personal, who have signed the Site Personnel Signature and Delegation List and Clinical Investigation Training Log. The delegated site personal will be required to complete e-learning prior to system access. Delegated personal will receive credentials.

It is the responsibility of the principal investigator that all data is entered promptly and correctly.

7.5 Concomitant treatment

Concomitant medication, related to urinary function (assessed by principal investigator) and pain management, taken from the time of consent through the study, until termination will be registered in the eCRF in the concomitant medication section.

To the extent possible – the subjects should not have changed their medication the last 24 hours before visit 1, 2 and 3. Any changes in medicine related to urinary function (assessed by principal investigator) and pain management, should be recorded under concomitant medication.

8 Risk – benefit analysis and ethical considerations

8.1 Risk-benefit analysis of the investigational device

A risk management process has been performed in accordance with the requirements stated in ISO 14971:2019 and in accordance with internal Coloplast procedures, including design verification, validated test methods, risk analysis and completion of a biological evaluation report for the investigational device.

Risks have been proven minimized or eliminated through appropriate risk control measures, confirmed by pre-clinical bench, laboratory, and biological safety evaluations.

The following risks will be mitigated by actions during the clinical investigation.

- Urinary tract infection. The subject is instructed to contact the principal investigator or delegate in case the subject is in doubt if they have a UTI or have symptoms of UTIs, mild pain or bleeding. If seen, this will be discussed with the principal investigator or delegate.

To mitigate and reduce the risks, the principal investigator/designees will be trained, according to the IFU, in use of the device.

8.2 Risk-benefit for subjects participating in the clinical investigation

The investigation is conducted in accordance with current law and applicable standards, see section 15. Statement of Compliance. The rights, safety and well-being of human subjects shall prevail over the interest of science of society.

The catheterisation of subjects, with both investigational device and the comparator will be performed by experienced urology nurses at sites with many years of experience in conducting IC and with previous experience in working with clinical investigations.

Risks associated with the investigation may be discomfort or stinging in the urethra during the catheterisation and additional risk of micro-trauma after catheterisation, which is expected to heal within 1-3 days. Hence, the risks are considered equal to the use of intermittent catheters already on the market.

To mitigate and reduce these risks, principal investigator or delegate will be trained, according to the IFU, in correct handling and catheterisation of the principal investigator and comparator device. The investigational setting is not expected to result in increased frequency or severity of the known risks associated with urethral catheterisation.

There are no direct benefits for the subjects involved; but, by participating in this investigation, the subjects will contribute with important information for developing improved solutions for urinary IC that in turn may benefit individuals who are dependent on catheters for emptying their bladder. The subjects will be compensated for the time spent (see section 17.2).

For further information on Adverse Events for this study please refer to section 18.

8.3 Risk Analysis for the conduct of the clinical investigation

A risk assessment of the clinical investigation will be conducted prior to the first subject enrolment and periodically re-assessed based on any new risks identified through the process. This assessment will be completed throughout the duration of the investigation, as defined by the study team.

8.4 Delegation of responsibility

Before initiation of the clinical investigation, sponsor must be provided with key personnel signed and dated curriculum vitae (not more than 2 years old) to verify their qualifications. Key site personnel are those, who treat or evaluate subject data in the clinical investigation. Also, the sponsor will ensure that all site personnel are trained in the investigation procedures, how to complete the CRFs, procedure for reporting an adverse event or serious adverse event (how, when, to whom), and who to contact in case of emergency related to the investigational device.

9 Monitoring Plan

The sponsor is responsible for ensuring appropriate monitoring of the clinical investigation activities.

The monitors will be the primary contact for the principal investigator and clinical investigation site personnel.

The monitoring of this Clinical Investigation can be delegated by the sponsor to a Clinical Research Organisation (CRO). The monitors will be the primary contact for the Principal Investigator and clinical investigation site personnel.

Monitoring activities are mandatory as per good clinical practice, however the extend and depth of these activities depend on the criticality of the clinical investigation, speed of enrolment, the experience of the clinical investigation site personnel in carrying out clinical investigations and specific study designs.

The data collected throughout the investigation and the conduct of the investigation, will be monitored according to the Monitoring Plan to ensure and verify, that the rights and well-being of the subjects are protected, that the data are accurate, complete and verifiable from source documents and that conduct of the investigation complies with the approved CIP, subsequent amendments (if any), ISO14155:2020 and the applicable regulatory requirements.

The monitoring will be conducted periodically at all sites by qualified personnel.

The principal investigator must be available for and agrees to cooperate with Coloplast Clinical Managers (CM) and/or the Clinical Research Associates (CRA) during their visits and ensure, that they have direct access to all documents required, including direct access to subjects' files, to ensure thorough monitoring.

The investigation can be subject to internal audits, if relevant. All monitoring visits and possible audits will be followed by internal reports and corrective actions, if needed. Follow-up letters will be forwarded to sites after all visits and any findings should be addressed by the principal investigator or delegate.

To ensure proper conduct of the investigation the following on-site or remote visits will be performed during the investigation:

- Site selection visit
- Site initiation visit
- Periodic monitoring visits
- Close out visit

9.1.1 Site selection visit

Depending on the prospective clinical investigation sites experience with the specific investigational device, an on-site qualification or site selection visit shall be performed, during which the feasibility of the clinical investigation requirements will be discussed and common agreement between sponsor and principal investigator shall be reached. This visit may also be replaced by one or more phone calls, if the principal investigator is known to the sponsor.

